## 2.2. Visit Windows

Nominal visits will be used for all by-visit analyses in the study. The study visits scheduled post randomization should occur at the times delineated in the Schedule of Activities. The study visits through Week 36 should occur within  $\pm 3$  days of the scheduled visit. The sponsor must be contacted for any significant deviation in the scheduling of a visit outside the appropriate window and determine how the participant should resume his/her normal dosing schedule relative to the baseline visit (Week 0).

## 2.3. Pooling Algorithm for Analysis Centers

Unless otherwise specified, data from all investigational centers/sites will be pooled for analyses.

## 2.4. Analysis Sets

There will be two database locks at Weeks 16 and 36 respectively.

## Week 16 database lock

Week 16 database lock will include selected efficacy and safety data through Week 16 and PK data through Week 16 for all randomized and treated participants. The data will be primarily used in planning for future bermekimab clinical development in HS. The selected efficacy and safety data include but not limited to following:

- 1. Lesion count [includes Hidradenitis Suppurativa Clinical Response (HiSCR)]
- 2. Numeric Rating Scale for Pain & Itch (NRS Pain & Itch) score
- 3. HS Symptom Diary (HSSD) HS related Pain Symptom Score
- 4. Baseline Disease Characteristics for 1-3 above
- 5. Demography
- 6. AE

## Week 36 database lock

Week 36 DBL would include all data through Week 36 for all randomized and treated participants.

## 2.4.1. Efficacy Analysis Set(s)

## 2.4.1.1. Full Analysis Set

The full analysis set (FAS) includes all randomized participants who received at least 1 dose of study agent. This analysis set will be used for the efficacy analyses of the endpoints through Week 36, *unless otherwise specified*.

In the efficacy analyses, participants will be analyzed according to the randomized treatment groups they were assigned to, regardless of the treatments they actually received.

## 2.4.1.2. Per Protocol Analysis Set

The primary endpoint will also be analyzed using the per-protocol population, which includes participants who are generally compliant with the protocol.

Specifically, the per protocol population includes participants in FAS except those

- who did not meet the inclusion criteria 7 in the protocol as listed below:
  - A total body count of abscesses and inflammatory nodules (A+N) of at least 3.
- who met the exclusion criteria 10 in the protocol as listed below:
  - Has a draining fistula count of >20 at the baseline visit.
- who did not receive all scheduled study agent administrations prior to Week 12.

However, for those who discontinued the study agent prior to Week 12 will be included in the perprotocol analysis and the data handling rule specified in Section 5.2.2 will apply. Participants who were excluded from the per protocol analyses will also be summarized.

## 2.4.2. Safety Analysis Set

The safety analysis set includes all randomized participants who received at least 1 dose of study agent, i.e., the treated population.

## 2.4.3. Pharmacokinetics Analysis Set

The pharmacokinetic (PK) analysis set includes all participants who received at least 1 complete dose of bermekimab and had at least 1 valid blood sample drawn for PK analysis after their first dose of bermekimab.

## 2.4.4. Pharmacodynamics Analysis Set

The Pharmacodynamics (PD) analysis set includes all participants who received at least 1 dose of bermekimab and had at least 1 valid blood sample drawn for PD(including IL-6) analysis after their first dose of bermekimab.

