- Assessment of Pharmacokinetics (PK)
- Reduction in serum IL-6 from baseline to week 32
- Reduction in serum IL-6 from baseline to week 16
- Reduction in serum IL-6 from baseline to week 12
- Reduction in serum IL-6 from baseline to week 8

Exploratory Endpoints:

- Change from baseline to week 32 in International Hidradenitis Suppurativa Severity Score System (IHS4)
- Change from baseline to week 16 in International Hidradenitis Suppurativa Severity Score System (IHS4)
- Change from baseline to week 32 in Hidradenitis Suppurativa Quality of Life Measure (HiSQOL)
- Change from baseline to week 16 in Hidradenitis Suppurativa Quality of Life Measure (HiSQOL)
- Change from baseline to week 32 in Physician's Global Assessment of Inflammatory Skin Disease (PGA-ISD)
- Change from baseline to week 16 in Physician's Global Assessment of Inflammatory Skin Disease (PGA-ISD)

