## 1.2. Trial Design

This is a randomized, double-blind, placebo-controlled study to further establish the efficacy and safety and explore dose effects for bermekimab monotherapy in adults with moderate-to-severe HS. It is anticipated that approximately 50% of patients enrolled will have failed prior targeted biologic therapy(ies) and approximately 50% will be naïve to these forms of biologic therapy in each arm. Patients will be assessed for study eligibility at the initial screening visit after providing informed consent. Thirty days are allowed in the screening window to complete all screening procedures and randomize the participant. During the screening period, certain treatments will be washed out, as applicable, according to eligibility requirements. Patients who fail initially may be re-screened once based on the investigator discretion but only if inclusion criteria are met at time of re-screening.

The study is approximately 40 weeks (30-day screening period, 32-week treatment period and a 4-week follow-up period) for all participants.

A diagram of the study flow (Figure 1) is provided below. Approximately 150 patients who meet eligibility criteria at screening will be randomized in a 1:1:1 fashion to one of three treatment arms:

**Bermekimab 400 mg SC (qw) (Treatment Arm 1)**: 800 mg loading dose of bermekimab (2 x 400 mg SC injections) at weeks 0 and 1 followed by weekly (qw) subcutaneous (SC) injections of 400 mg bermekimab through week 31

**Bermekimab 400 mg SC (q2w) (Treatment Arm 2)**: 800 mg loading dose of bermekimab (2 x 400 mg SC injections) at weeks 0 and 1 followed by subcutaneous (SC) injections of 400 mg bermekimab every other week (q2w) alternating with matching placebo q2w through week 31.

**Placebo (Treatment Arm 3)**: 4mL loading dose of placebo (2 x 2mL SC injections) at weeks 0 and 1 followed by weekly placebo injections from week 2 through week 15. Patients in Arm 3 will begin to receive weekly (qw) blinded subcutaneous (SC) injections of 400 mg bermekimab beginning at week 16 through week 31.

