#### 7.3. Biomarkers

Biomarker assessments will include the evaluation of relevant markers in serum for all participants. The samples will be used to better understand the biology of HS in some or all of the following ways: to provide mechanistic assessment of the pharmacodynamic response of participants to treatment with bermekimab, to analyze differences between responders and nonresponders, and to determine if the markers might be used to classify participants as potential responders prior to treatment.

Serum samples will be analyzed for circulating factors such as cytokines and other inflammatory markers (eg, IL-17A, IL-17F, IL-23, TNF $\alpha$ , IL-6, IL-22), and other categories of biomarkers potentially associated with the development and progression of HS or related to the bermekimab mechanism of action. These analyses are considered exploratory and will be summarized in a separate biomarker technical report.

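### The SAP's pharmacodynamic set admits placebo participants only after crossover and a later sample, so an IL-6 summary on it would select the control arm after randomization.

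*SAP*

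**What the plan says.** SAP 2.4.4 sets two conditions. The first is exposure: "The Pharmacodynamics (PD) analysis set includes all participants who received at least 1 dose of bermekimab". The second is a sample: the participant must also have "had at least 1 valid blood sample drawn for PD(including IL-6) analysis after their first dose of bermekimab". The exposure condition names bermekimab. SAP 2.4.1.1 uses the wider term, so placebo participants belong to that set from Week 0: "The full analysis set (FAS) includes all randomized participants who received at least 1 dose of study agent".

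The placebo arm first receives bermekimab at crossover (SAP 1.2): "Patients in Arm 3 will begin to receive weekly (qw) blinded subcutaneous (SC) injections of 400 mg bermekimab beginning at week 16 through week 31".

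Protocol 3.1 lists IL-6 among the secondary endpoints at four times. Three fall in the placebo-controlled period: "Reduction in serum IL-6 from baseline to week 8", "Reduction in serum IL-6 from baseline to week 12" and "Reduction in serum IL-6 from baseline to week 16". The fourth is Week 32.

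SAP 7.3, the only SAP section that describes analysis of serum markers, includes IL-6 in its list and takes a different population: "Biomarker assessments will include the evaluation of relevant markers in serum for all participants". It cites no analysis set, calls the work exploratory and places it in a separate report. Protocol 10.5.4 plans descriptive statistics for PD.

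**The concern.** Requiring bermekimab exposure makes sense for drug concentrations and anti-drug antibodies, and SAP 2.4.3 and 2.4.5 use it there. IL-6 is different. Placebo participants have IL-6 values, and their blood is drawn on the same calendar. Their change over Weeks 0 to 16 is what separates a drug effect from natural course and regression to the mean.

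Under SAP 2.4.4, whether a placebo participant's Week 8 or Week 12 value counts depends on what happens later: staying to Week 16, taking the crossover dose and giving another sample. The bermekimab arms face no such condition. This is selection after randomization in one arm only. If early placebo leavers differ in IL-6 change from those who stay, the displayed placebo mean is shifted.

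PD evaluation is a secondary objective in SAP 1.1, and Protocol 1.2 presents IL-6 as a candidate PD measure of response. A by-arm display with an intact control is therefore worth having, even without a test.

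**Working it through.** **The plan's own figure.** Neither document gives a number for the IL-6 endpoints or the PD set. The only sample-size figure is for HiSCR (Protocol 10.1, SAP 1.4): 60% against 30%, two-sided 0.05, 80% power.

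n = [1.960 × √(2 × 0.45 × 0.55) + 0.842 × √(0.6 × 0.4 + 0.3 × 0.7)]² / 0.30² ≈ 42 per arm, or 126 in total. Power at 42 per arm is 0.800, so the figure reproduces. It is used here only for scale: about 150 randomized gives about 50 per arm, and the margin is 1 − 126/150 = 16%. The plan says this margin also serves safety data, so it is not a stated dropout rate.

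**When each arm can qualify** (Protocol 5.1 and 5.2). PD draws are scheduled at Weeks 0-5, 8, 12, 16, 24, 32 and 36. The Week 16 draw is listed before the injection.

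| | First bermekimab dose | First scheduled PD draw after it |
|---|---|---|
| Bermekimab arms | Week 0 | Week 1 (day 7) |
| Placebo arm | Week 16 (day 112) | Week 24 (day 168) |

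The early-termination and unscheduled visits also allow a PD draw, so a placebo participant who crosses over and leaves before Week 24 can still qualify. A placebo participant who leaves before crossover cannot, because no bermekimab dose has been given.

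**What the rule removes.** The table applies SAP 2.4.4 to participants dosed and sampled on schedule while in the study. Every bermekimab participant in these rows stays in the set after a Week 1 sample.

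| Participant leaves | Placebo in set? | Placebo values lost because of the rule |
|---|---|---|
| Before Week 8 | No | None at Weeks 8, 12 or 16 (none collected) |
| Weeks 8 to 12 | No | Week 8 |
| Week 12 to crossover | No | Weeks 8 and 12 |
| After crossover, no later sample | No | Weeks 8, 12 and 16 |
| After crossover, with a later sample | Yes | None |

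Participants who leave before crossover normally have no Week 16 sample, so their loss at that week is about zero. In a data cut through Week 16, no placebo participant treated as randomized has a qualifying scheduled draw.

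**Size, by assumption.** If 10-20% of 50 placebo participants leave before crossover, that is 5-10 people. This count includes those who leave before Week 8, or before Week 12, and so have no value there to lose. It is therefore a rough ceiling for early leavers at Weeks 8 and 12. Participants who cross over but give no later sample would be additional.

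Let d be the share of placebo participants with a value at a given week whom the rule excludes, with all 50 per arm taken to have a value. Then m = 50(1 − d) remain, and the standard error of an arm difference is multiplied by √[(1/50 + 1/m)/(2/50)]. If the excluded differ from the retained by k SD in IL-6 change, the placebo mean shifts by d × k.

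| d (assumed) | m | SE factor | Shift, k = 0.25 | k = 0.5 | k = 1 |
|---|---|---|---|---|---|
| 0% | 50 | 1.000 | 0 | 0 | 0 |
| 8% | 46 | 1.022 | 0.02 SD | 0.04 SD | 0.08 SD |
| 16% | 42 | 1.047 | 0.04 SD | 0.08 SD | 0.16 SD |
| 24% | 38 | 1.076 | 0.06 SD | 0.12 SD | 0.24 SD |
| 30% | 35 | 1.102 | 0.075 SD | 0.15 SD | 0.30 SD |

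Both d and k are assumptions, and the documents do not indicate the direction of any shift.

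**The case against.** The strongest reply is that no analysis is tied to this set. SAP 7.1 names the PK set and SAP 7.2 the immunogenicity set, but SAP 7.3 names none and speaks of all participants. If the analyst follows SAP 7.3, nothing is lost. This stands as a limit: the consequence is conditional. It does not remove the problem, because SAP 2.4.4 names IL-6 explicitly, no other set is assigned to IL-6, and the two sections give different populations.

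A second reply is that little depends on it. IL-6 is absent from the modelled endpoints in Protocol 10.5.3.2 and from the SAP 5.4 list, and the output is descriptive or exploratory. This also stands. A reader might infer that a planned comparison with placebo is invalidated, but the documents plan none.

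Two further inferences go too far:

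- **That all placebo samples at Weeks 8, 12 and 16 are discarded.** SAP 2.4.4 restricts participants and does not restrict samples. Nothing in it removes the earlier samples of someone who later qualifies. The control disappears only in a cut through Week 16, and the listed contents of the Week 16 lock (SAP 2.4) do not name IL-6 or PD, although that list is not exhaustive.
- **That 5-10 placebo participants are lost at each of the three weeks, against almost none in each bermekimab arm.** Early leavers in any arm have no later values under any definition. What the rule adds is the loss of placebo values already collected.

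**Conclusion.** The point holds in conditional form. If IL-6 is summarised on the SAP 2.4.4 set, the placebo control is selected by post-randomization events that the bermekimab arms do not face, and SAP 2.4.4 conflicts with SAP 7.3. The values at risk belong to placebo participants who leave between Week 8 and crossover (Week 8 summary) or between Week 12 and crossover (Week 12 summary), plus any who cross over without a later sample.

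The likely effect is modest. If the rule excluded 16% of placebo values and the excluded differed by 0.5 SD, the placebo mean would move by 0.08 SD and the standard error would rise by about 5%. Both inputs are assumptions. The primary HiSCR analysis uses the full analysis set and is untouched. The change is worth making because the definition is wrong for its purpose and costs almost nothing to correct.

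A separate inconsistency remains: the protocol lists IL-6 as secondary, while SAP 7.3 treats the marker analyses as exploratory.

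**What to change.** In SAP 2.4.4, define the PD set as every randomized participant given one or more doses of study agent, whether bermekimab or placebo, with a valid PD sample after the first dose. All arms then qualify on the same terms from Week 1. Cite this set in SAP 7.3 so that the two sections agree. State that IL-6 is summarised by randomized arm through Week 16, with the pre-injection Week 16 value counted under placebo, and that the placebo-to-bermekimab group is shown separately afterwards. SAP 5.2.3 already uses that layout for efficacy, and SAP Section 6 uses a similar one for safety.

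The cost is one redefined sentence, one cross-reference and a line on presentation. No visit, sample or sample size changes, because placebo blood is already drawn at these weeks. The PK and immunogenicity sets can stay as they are.

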## 2.4.5. Immunogenicity Analysis Set

The immunogenicity analysis set includes all participants who received at least 1 dose of bermekimab and who have at least 1 sample obtained after their first dose of bermekimab for the detection of antibodies to bermekimab.

## 2.5. Definition of Subgroups

To evaluate the consistency in the primary efficacy endpoint (proportion of participants who achieve HiSCR at Week 12) over demographics, baseline disease characteristics, and prior HS medication use, subgroup analyses will be performed when sample sizes are permitted. The subgroups include, but are not limited to, the following:

#### **Baseline demographics:**

- Sex (male, female)
- Race
- Baseline Age (<40 years, 40 to <65 years,  $\geq$ 65 years)
- Baseline weight (< median,  $\geq$  median)
- BMI (Normal [<25], Overweight [25 -<30], Obese [≥ 30])

#### **Baseline disease characteristics:**

- Baseline Hurley stage status (II, and III)
- Age at diagnosis (years) (< median,  $\geq$  median)
- HS disease duration (years) (< median,  $\geq$  median)
- Baseline AN count category (3 to 5, 6 to  $10, \ge 11$ )
- Baseline AN count (< median,  $\ge$  median)
- Baseline HS-PGA (<3, 3, 4, 5)
- Baseline C-reactive protein (CRP) level (< median,  $\ge$  median)
- Baseline Erythrocyte Sedimentation Rate (ESR) (< median,  $\ge$  median)

#### HS medication:

- Prior biologic therapy used
  - Never used
  - Ever used

## 2.6. Study Day and Relative Day

Study day is defined as the number of days from the study reference date to the event/visit date. It will be calculated as follows:

- If the event/assessment occurs on or after the reference date, then study day = event/assessment date reference date + 1.
- If the event/assessment occurs before the reference date, then study day = event/assessment date reference date.

Hence, the day of reference date is Study Day 1; the previous day is Study Day -1.

#### 2.7. Baseline and Endpoint

In general, the baseline measurement is defined as the closest measurement taken prior to or at the time of the first study agent administration date unless otherwise specified.

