 - Adverse event monitoring
 - Concomitant medications/treatments

Visit 9 (Week 8) (day 56 +/-3):

- At least 45 minutes before injection: Remove syringe from refrigeration and lay flat; allow to warm to room temperature. Do not heat
- Pre-injection
 - Patient Diary
 - Vital signs, Urine Pregnancy
 - Urinalysis
 - Blood draw for chemistry, hematology, inflammation markers, PK/ADA, IL-6, PD, biomarker and research analysis
- Bermekimab/placebo subcutaneous injection
- Post-injection
 - Adverse event monitoring
 - Concomitant medications/treatments

Visit 12 (Week 11) (day 77 +/-3):

- At least 45 minutes before injection: Remove syringe from refrigeration and lay flat; allow to warm to room temperature. Do not heat
- Pre-injection
 - Patient Diary
 - Physical Exam, Vital signs, Urine pregnancy
- Bermekimab/placebo subcutaneous injection
- Post-injection
 - Adverse event monitoring
 - o Concomitant medications/treatments

Visit 13 (Week 12) (day 84 +/-3):

- At least 45 minutes before injection: Remove syringe from refrigeration and lay flat; allow to warm to room temperature. Do not heat
- Pre-injection
 - Patient Diary
 - o HiSCR, mHSS, HS-PGA, PGA-ISD, IHS4 and Hurley Staging
 - o DLQI, HADS, PGI-c, PGI-s, EQ-5D-3L, HSSD, HiSQOL
 - Physical Exam, Vital signs, Urine pregnancy
 - Blood draw for chemistry, hematology, inflammation markers, PK/ADA, IL-6,
 PD, biomarker and research analysis
- Bermekimab/placebo subcutaneous injection
- Post-injection
 - Adverse event monitoring
 - Concomitant medications/treatments

BLINDED ACTIVE DOSING PERIOD

Visit 17 (Week 16) (day 112 +/-3):

- At least 45 minutes before injection: Remove syringe from refrigeration and lay flat; allow to warm to room temperature. Do not heat
- Pre-injection
 - o Patient Diary
 - o HiSCR, mHSS, HS-PGA, PGA-ISD, IHS4 and Hurley Staging
 - DLQI, HADS, PGI-c, PGI-s, EQ-5D-3L, HSSD, HiSQOL

- o Physical Exam, Vital signs, Urine pregnancy
- Blood draw for chemistry, hematology, inflammation markers, PK/ADA, IL-6,
 PD, biomarker and research analysis
- o Urinalysis
- Bermekimab/placebo subcutaneous injection
- Post-injection
 - Adverse event monitoring
 - Concomitant medications/treatments

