⁴ Assessments/procedures should be conducted in the following order: patient assessments, investigator assessments, safety and laboratory assignments, administration of the study drug.																		
⁵ Concomitant medications within 30 days before screening until 7 days after the last administration of the study drug must be recorded for the purpose of drug-drug and drug-disease interaction evaluation and signal detection																		

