8. STUDY VARIABLES

8.1 DEMOGRAPHIC AND DISEASE CHARACTERISTICS

Demographic characteristics will include standard demography (age, sex, race, height, weight, and BMI) medical history, medication history, and prior biologic use for each patient. Characteristics of the patients with hidradenitis suppurativa, including duration of disease, baseline disease severity scores (HiSCR, Modified Hidradenitis Suppurativa Score, Hurley Staging and Hidradenitis Suppurativa Physician's Global Assessment, Physician's Global Assessment of Inflammatory Skin Disease), and baseline patient reported outcomes (PGI-c, PGI-s, NRS Pain, NRS Itch, EQ-5D-3L, HADS, HSSD, HiSQOL, IHS4 and DLQI), will be collected. Baseline is defined as the visit 1 (week 0), pre-injection assessment.

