## Summaries through Week 16 (placebo controlled):

Safety data through Week 16 will be summarized by treatment groups

- 1. Placebo
- 2. Bermekimab 400 mg q2w
- 3. Bermekimab 400 mg qw
- 4. Combined Bermekimab

This allows between-group comparisons of safety between the bermekimab regimens and the placebo group based on similar follow-up period in each group.

#### Summaries through Week 36

Safety data through Week 36 will be summarized by treatment groups including

- 1. Placebo  $\rightarrow$  bermekimab 400 mg qw
- 2. Bermekimab 400 mg q2w
- 3. Bermekimab 400 mg qw
- 4. Combined Bermekimab

This allows safety comparisons between each bermekimab regimen through Week 36 based on the similar follow-up time in each group.

The list of actual treatment groups for safety analyses and inclusions of participants and safety events/measurements in each group are defined as follows:

- 1. **Placebo:** all participants who were randomized to placebo at Week 0 and received treatment with placebo only or received treatment with placebo prior to receiving treatment with bermekimab. For participants who started treatment with placebo but later received bermekimab, the safety events/measurements on and after the first dose of bermekimab will be excluded from this group. Only the safety events/measurements that occurred while the participants had been receiving placebo only will be included in this group.
- Placebo → bermekimab 400 mg qw: All participants who were randomized to placebo at Week 0 started treatment with placebo only and later crossed over to receive treatment with bermekimab 400 mg SC (qw). Only the safety events/measurements from these participants that occurred on and after their first administration of bermekimab will be included in this group.
- 3. **Bermekimab 400 mg q2w:** all participants who were randomized to bermekimab 400 mg SC (q2w) at Week 0 and received bermekimab. All the safety events/measurements from these participants that occurred from Week 0 will be included in this group.
- 4. **Bermekimab 400 mg qw:** all participants who were randomized to bermekimab 400 mg SC (qw) at Week 0 and received bermekimab. All the safety events/measurements from these participants that occurred from Week 0 will be included in this group.

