## 6.3. Vital Signs and Physical Examination Findings

Vital signs including pulse, blood pressure (systolic and diastolic), body temperature, peripheral blood oxygen saturation (SpO2) and respiratory rate will be measured at visits (pre-injection and

post-injection) as per the schedule of activities in the protocol. Descriptive statistics of the observed value and change from baseline of the vital signs will be summarized by treatment group over time.

Physical exam findings will not be analyzed. When physical exam findings are captured as AEs, those will be included in the analyses of AEs.

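### The crossover safety column holds only data from first bermekimab onward, but measures laboratory and vital-sign change from a Week 0 baseline taken before placebo

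*SAP*

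**What the plan says.** **Baseline.** The SAP 2.7 rule is "the baseline measurement is defined as the closest measurement taken prior to or at the time of the first study agent administration date". It applies in general and leaves room for exceptions. Protocol 8.1 agrees: "Baseline is defined as the visit 1 (week 0), pre-injection assessment".

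**Crossover.** SAP 1.2: "Patients in Arm 3 will begin to receive weekly (qw) blinded subcutaneous (SC) injections of 400 mg bermekimab beginning at week 16 through week 31".

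**Safety columns.** In the group definitions of SAP 6, once a placebo participant has started bermekimab, "the safety events/measurements on and after the first dose of bermekimab will be excluded from this group", meaning the Placebo column. The Placebo → bermekimab 400 mg qw column takes only what occurs from that participant's first bermekimab administration onward, and it appears in the through-Week-36 summaries.

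**Displays.** SAP 6.3: "Descriptive statistics of the observed value and change from baseline of the vital signs will be summarized by treatment group over time". SAP 6.2 plans box plots of selected laboratory values and of their change from baseline. Protocol 10.5.2.2 asks for actual values and change from baseline by treatment group for both kinds of data.

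SAP 6 to 6.3 do not use the exception left open in 2.7, so no separate baseline is given for participants who cross over.

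**The concern.** The column's data window opens at Week 16, but the reference value for its change scores is taken at Week 0. A reader of the Week 36 tables will naturally take change in a column restricted to bermekimab data as change since bermekimab started. Here it also contains whatever happened during 16 weeks on placebo.

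Some movement in that period is plausible from the protocol itself. Several HS treatments are washed out before entry (Protocol 4.2). Analgesics, and for those who qualify rescue antibiotics, may start after baseline (Protocol 2.11.1 and 2.11.2). A laboratory or vital-sign shift that arose on placebo could be taken for a drug signal, and a real change on drug could be masked by an opposite shift before it.

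The column may hold up to about 50 participants (150 randomized 1:1:1, 150/3 = 50).

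**Working it through.** **Inputs**
- Baseline: Week 0 pre-injection (SAP 2.7, Protocol 8.1).
- Study agent is not limited to bermekimab. SAP 2.4.2: "The safety analysis set includes all randomized participants who received at least 1 dose of study agent, i.e., the treated population". The placebo arm belongs to that set, so its first study agent dose is the Week 0 placebo.
- First bermekimab in Arm 3: Week 16 (SAP 1.2), which is day 112 in Protocol 5.1.
- Scheduled chemistry and hematology: Weeks 0, 8, 12, 16, 24, 32 and 36 (Protocol 5.2 calendars). After crossover: Weeks 24, 32 and 36.
- Vital signs: every weekly visit through Week 32, then Week 36.

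**Step 1: reproduce the plan's own figure.** 16 weeks × 7 = 112 days, which matches the protocol's day for Visit 17. The gap from baseline to first bermekimab is 16 weeks.

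**Step 2: split the displayed change.** Write Y(w) for the value at Week w. For a crossover participant,

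Y(w) − Y(0) = [Y(16) − Y(0)] + [Y(w) − Y(16)].

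The first bracket is change on placebo and the second is change on bermekimab. The plan displays the sum.

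**Step 3: share of elapsed time on placebo = 16/w.**

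| Laboratory visit | Weeks since baseline | Weeks since first bermekimab (w − 16) | Placebo share of time |
|---|---|---|---|
| Week 24 | 24 | 8 | 16/24 = 67% |
| Week 32 | 32 | 16 | 16/32 = 50% |
| Week 36 | 36 | 20 | 16/36 = 44% |

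Vital signs also fall between these visits. The share is 16/20 = 80% at Week 20 and 16/28 = 57% at Week 28.

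**Step 4: what the share means.** Suppose a measure moves by 1 unit during placebo and not at all afterwards. The column then shows 1 unit at Weeks 24, 32 and 36 alike, although nothing changed on bermekimab. With the Week 16 pre-injection value as reference it shows 0 at each. The size of the distortion is therefore the placebo-period change itself. The documents do not give that change, so it cannot be computed.

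**Step 5: is the needed value available?** Yes. Protocol 5.1, Visit 17, schedules chemistry, hematology, inflammation markers and vital signs before the injection. The calendar footnote in Protocol 5.2.1 gives the order of procedures as "patient assessments, investigator assessments, safety and laboratory assignments, administration of the study drug". With that reference, the placebo share is 0% at every later visit.

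**The case against.** The strongest defence is that one Week 0 baseline is a legitimate choice. It gives all columns of the Week 36 table the same reference, before any study treatment. The column label shows the placebo start, SAP 6 plans no formal safety comparison, and observed values are shown beside the changes. Adverse event counts, observed values and the worst-toxicity-grade summary are not change-from-baseline displays. All of this stands and limits the weight of the point. It does not remove the mismatch. Change since Week 0 answers a different question from the one posed by a column confined to data from first bermekimab onward. Observed levels do not replace a within-participant change, because the pre-drug Week 16 level sits in a different column and table.

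A reader might infer two stronger things, which the documents do not support.

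- *That the Week 16 pre-injection values are moved into the bermekimab column, so that Placebo loses its Week 16 laboratory control.* This needs a cut by calendar date. The group definitions name an event, the first dose, and a sample drawn before that dose is not on or after it. The next sentence of the Placebo definition keeps what occurred while participants were on placebo only. SAP 6.1 uses clock times on the first-dose day, SAP 6.3 separates pre- from post-injection vital signs, and Protocol 5.2.1 lists Week 16 in the placebo-controlled calendar. What remains is that the SAP never says outright that the cut is by time. That matters because Visit 17 has vital signs both before and 30 minutes after the injection.
- *That 67%, 50% or 44% of the displayed change is bias.* These are shares of elapsed time. Actual drift could be nil, or could account for the whole displayed change.

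**Conclusion.** The point holds for the baseline. In the Placebo → bermekimab 400 mg qw column, laboratory and vital-sign change from baseline mixes 16 weeks on placebo with 8, 16 and 20 weeks since first bermekimab at Weeks 24, 32 and 36. The numerical distortion is unknown and depends on how far each measure moved on placebo.

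The effect is confined to descriptive change-from-baseline displays for one column. SAP 6 does not define its Combined Bermekimab column in terms of crossover participants. If they are included there, the same mixture carries into that column.

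The conclusion assumes that the SAP 2.7 rule is applied as written and that first bermekimab is given at Week 16 as scheduled. This is a cheap improvement to how the crossover data are displayed. It does not threaten the safety analysis as a whole.

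**What to change.** In SAP 2.7 and SAP 6, state that for the Placebo → bermekimab 400 mg qw column, laboratory and vital-sign change from baseline is taken from the last value before the first bermekimab injection, normally the Week 16 pre-injection value. Footnote the tables to say that this baseline differs from the Week 0 baseline of the other columns. The change from Week 0 may be kept as a secondary display.

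As a clarification only, state that data are divided between Placebo and Placebo → qw by the time of the first bermekimab injection. Visit 17 pre-injection laboratory and vital-sign values then stay in Placebo. Adverse events on that day with a missing time go to Placebo → qw, in line with how SAP 6.1 treats the day of the first study agent dose.

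The cost is a few SAP sentences, one derivation flag and a footnote. The values are already scheduled, so no visit or sample is added and no efficacy analysis changes. The drawback is that one table will carry two baselines, which the footnote must make plain.
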